### **6.3. Inclusion criteria**

People with dry AMD are included regardless of age. Thus, this value is given as 20-99 years.

### **6.4. Exclusion criteria**

Exclusion criteria are wet AMD, epilepsy and double vision. Other eye diseases are not a problemrepresent.

## **7. Medical examinations**

### **7.1. Personal data**

Only the age is recorded.

### **7.2. anamnese**

Duration of illness, previous therapies.

### **7.3. Clinical examination**

OCT, eyesight, eye status.

### **7.4. Measurement parameters**

Eyesight, fundus.

### **7.5. type of application**

Therapy will from the patient Carried out independently daily and takes 90 seconds per eye.

## **8. Treatment of the subjects**

### **8.1. Admission to the study**

All participants are informed about the study, effects, side effects and risks by means of an information sheet written for the study together with the supervising doctor. Consent is given by mutual signature with clarity and consent.

### **8.2. Hospitalization**

no

### **8.3. Companion therapy**

None

### **8.4. documentation**

The encrypted data can only be viewed and further processed by the examiner. It'll be a complete oneA.nanonymization of the original data is carried out after the data collection has ended. The study will be at<https://clinicaltrials.gov>registered and dealt with according to the specifications. These defaults are also used for the publication.

### **9.2. Recording of compliance**

By questioning

### **9.3. Risk-benefit assessment**

The first study showed a 34% improvement in eyesight as a result of the therapy; there were no side effects or undesirable effects.

### **9.5. Control body**

onGaround the studieconception nott provided.

### **9.6. Interim evaluation**

Not provided.

## **9.7. Termination criteria**

If undesirable results occur or at the request of the participants.

## **9.8. Abort the entire study**

For the good and in the interest of the test subjects, the investigator can terminate the study at any time if severe side effects or other unforeseeable circumstances occur. In this case, the ethics committee will be informed.

## **10.2. Biometric design**

Longitudinal comparison of the change

## **10.3. Sample planning**

According to the results of the first study, the calculation with the G \* Power system results in a number of 150 eyes. For the study, that number was doubled.

## **10.4. Data acquisition and evaluation**

Entry in Libre Office spreadsheet ® Evaluation in PSPP ®.

## **10.5. Statistical Methods**

T test, Wilcoxon, Smirnov

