### **3. Short version of the project**

With the Medical Eye Trainer (MET) training system, patients suffering from dry age-related macular degeneration (AMD) are treated as part of the clinical routine. The MET system is an application (software) for a standard multimedia device such as a smartphone or tabletC.computer. The people affected by the disease treat themselves independently once a day for 90 seconds. The planned study will not introduce any new indications or therapies. Only data from ongoing therapies are collected, around to check the effect of the treatment. It turns around a Non-interventional study (NIS). It doesn't come to any study-specific risk increase, since there are no study-related interventions that go beyond the clinical routine.

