## 4. Scientific background

### 4.1. General information

AMD is a disease of the eye that is widespread worldwide. According to the Gutenberg health study, around 7,000,000 people in Germany suffer from it. The figures for Austria can be assumed to be 700,000 due to the smaller population. A distinction is made between two forms of AMD, the wet form with 15% and the dry form with 85%. Both types have a high risk of developing significant visual impairment quickly. There are currently only a few therapeutic options for the dry form of the disease. Essentially, nutritional supplement therapy should be mentioned here. This treatment can only reduce the progression of deterioration in 10% of affected people, but it does have a significant side effect profile. This raises the question of completely different treatment approaches. Because of this, the Medical Eye Trainer (MET). This is a training device that can easily be used by yourself. The purpose of this new therapy is not to attempt to cure AMD. The eye and brain are trained to better deal with the disease. In a first study on 17 eyes, an improvement in visual performance could even be achieved in 11 cases, the remaining 6 cases showed a stable situation. In no case did it deteriorate. Thus it was possible for the first time not only to slow down this disease, but even to improve it. In a second study with a planned number of 150 examinations, this positive effect is to be investigated further. A calculation based on the results of the first study with G \* Power gives an optimal number of 150 examinations.

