### **5.3. Target parameters**

#### **5.3.1. Primary target point**

Eyesight improvement

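### The unit of analysis is not stated: the study is sized in eyes, nothing limits a person to one eye, and no clustered method is named

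*Combined protocol and SAP*

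**What the plan says.** - **Methods.** Section 10.5 reads in full "T test, Wilcoxon, Smirnov". Section 10.2 adds only that change is compared over time. Neither names the unit.
- **Sample size.** Sections 6.1 and 10.3 both say that the G*Power calculation "results in a number of 150 eyes. For the study, that number was doubled". No number of patients is given. Section 4.1 puts the total differently and without doubling: "In a second study with a planned number of 150 examinations, this positive effect is to be investigated further".
- **Basis of the calculation.** The first study is reported per eye (section 4.1): "In a first study on 17 eyes, an improvement in visual performance could even be achieved in 11 cases".
- **Who is enrolled.** Section 6.3 works by person: "People with dry AMD are included regardless of age". Sections 6.2 to 6.4 contain no rule on one eye, the worse eye or a designated study eye.
- **Training.** Section 3 says patients "treat themselves independently once a day for 90 seconds". Sections 7.5 and 9.1 describe the training as "Carried out independently daily and takes 90 seconds per eye". These statements need to be reconciled, but none of them says which eyes are analysed.
- **Primary target.** Section 5.3.1 says only "Eyesight improvement".

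Section 10.1 is not in the available text. The contents list gives its subject as the biometric authority and institution, so it is unlikely to define the unit.

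**The concern.** The t test and the Wilcoxon test assume independent units. Pairing before with after deals with two measurements on one eye; it does not deal with two eyes of one person. Those eyes share age, adherence to training, visit day and examiner, so a positive correlation between their changes is plausible, although the documents give no value.

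Because the sample is counted in eyes, as in the first study, the most natural way to carry out the plan is to enter every eye as a separate observation. If some patients then contribute both eyes and the changes are positively correlated, the evidence for the primary target is overstated. Leaving the unit open also allows it to be chosen after the data have been seen.

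**Working it through.** **The plan's own figure.** The 150 can be neither reproduced nor refuted, since alpha, power, effect size and standard deviation are not given. With a paired t test at an assumed two-sided 5% level and 80% power, 150 independent units correspond to a standardised change d of 0.23. Testing the first study's 11/17 improved against one half gives 70 to 145, depending on sidedness (one or two) and power (80 to 95%). No inter-eye correlation can be recovered from either route.

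**Inputs.** N = 300 eyes if the doubling is read as 2 × 150 (sections 6.1 and 10.3), or N = 150 if the section 4.1 figure is the total and its examinations are counted as eyes. Assumed, because the documents give no value: two-sided alpha 0.05; f, the share of *eyes* that come from two-eye patients; rho, the between-eye correlation of the change.

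**Formulas.** With f·N/2 two-eye patients, the variance of the mean of N eyes is (σ²/N)·(1 + f·rho). An eye-level test uses σ²/N. Hence:

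- design effect D = 1 + f·rho
- actual type I error = 2·(1 − Φ(1.96/√D))
- understatement of the standard error = 1 − 1/√D
- effective number of eyes = N/D
- patients = N·(1 − f/2)

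For f 0.5 and rho 0.5: D = 1.25, 1.96/√1.25 = 1.753, type I error 8.0%, and standard error understated by 1 − 1/1.118 = 10.6%.

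| f | rho | D | Type I error | SE understated | Effective eyes, N = 300 | Effective eyes, N = 150 |
|---|---|---|---|---|---|---|
| 0 | any | 1.00 | 5.0% | 0% | 300 | 150 |
| 0.25 | 0.2 | 1.05 | 5.6% | 2.4% | 286 | 143 |
| 0.5 | 0.5 | 1.25 | 8.0% | 10.6% | 240 | 120 |
| 1 | 0.5 | 1.50 | 11.0% | 18.4% | 200 | 100 |
| 1 | 1 | 2.00 | 16.6% | 29.3% | 150 | 75 |

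Because f counts eyes, f 0.5 means that one third of patients contribute two eyes: 0.25/0.75. If half of the *patients* do, f is 2/3; at rho 0.5 this gives D = 1.33 and a type I error of 9.0%. The number of patients lies between 150 and 300 if N = 300, and between 75 and 150 if N = 150.

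**Simulation.** Normally distributed changes with no true effect, 40,000 replicates, in the order of the table rows:

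- Eye-level t test: 5.0, 5.4, 7.8, 11.0 and 16.3% at 300 eyes; 4.9, 5.5, 8.0, 10.6 and 16.9% at 150 eyes.
- t test on one mean per patient: 4.7 to 5.1% throughout.

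The inflation depends on f·rho and not on N, and averaging within the patient removes it.

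**Power.** At d = 0.23, a correctly clustered analysis in the worst case (f 1, rho 1) has 80% power with 300 eyes (effective 150) and 50% with 150 eyes (effective 75).

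**The case against.** Section 10.5 is a list of test names and does not prescribe an eye-level analysis. Sizing in eyes is compatible with one eye per patient, and then nothing is inflated. Both f and rho are unknown, and the 16.6% is a bound that needs every patient to contribute two eyes and a correlation of exactly 1. On the plain reading of 300 eyes, the effective size never falls below the calculated 150, so a conclusion at the planned effect would probably survive. The 150-eye reading rests on a background section that speaks of examinations and most naturally repeats the undoubled figure. Finally, with no primary test or alpha set, fixing the unit alone does not define the primary inference.

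Most of this stands as a limit on size: the inflation is conditional, the bound is not an expected value, and the 300-eye reading deserves the greater weight. It does not remove the point. The plan gives no reason for the doubling, and a larger N leaves the type I error of an eye-level test unchanged. Nor does any available text rule out the entry of eye pairs.

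**Conclusion.** The concern holds and should be fixed. It is certain on the available text that the unit of analysis and the number of patients are unstated, that nothing limits a person to one eye, and that no patient-level or clustered method is named. The direction of the error is clear if correlated pairs are analysed eye by eye: the standard error is too small. Its size is not known. Under an assumed two-sided 5% level it runs from no inflation with one eye per patient to the 16.6% bound, with 8.0% to 11.0% for rho 0.5 and f between 0.5 and 1. If 300 eyes are meant, the consequence lies mainly in error rate and interval width, and power against the calculated 150 is protected. If the total is 150 eyes, power is also at risk.

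**What to change.** In section 10.5, state:

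> The patient is the unit of analysis. For patients with two study eyes the change is averaged over both eyes; patients with one study eye contribute that eye. The paired t test or Wilcoxon test is run on one value per patient.

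One study eye per patient, chosen by a rule fixed in advance, would also be acceptable, as would a mixed model or GEE clustered by patient. Averaging is the simplest, since it keeps the named tests and the software in section 10.4.

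In sections 6.1 and 10.3, give the planned number of patients as well as eyes, define which eyes of a person count as study eyes, and reconcile the 150 eyes, the doubling and the 150 examinations of section 4.1. Enter the data as one spreadsheet row per patient with right-eye and left-eye columns. The eyes then stay linked after the anonymisation planned in section 8.4, which needs no change.

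**Cost.** This takes wording, a spreadsheet layout, and an amendment added to each plan in circulation and reported to the ethics committee under section 11. No patients, visits or procedures are added. There are three statistical downsides:

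- The headline number is smaller.
- Intervals are wider than the eye-level ones. The ratio of standard errors is √(1 − f + f·(1 + rho)/4)/(1 − f/2), so they are wider by about 4% (f 0.25, rho 0.2), 11% (0.5, 0.5), 22% (1, 0.5) and at most 41% (1, 1). If rho were 0 and half of the patients had two eyes (f 2/3), the interval would be about 6% wider with no gain in error control.
- The mean becomes patient-weighted. At f 0.5, two-eye patients carry 33% of the weight instead of 50%, so the estimate shifts if their eyes respond differently from those of one-eye patients.

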## **11. Changes to the study plan**

Every change to the test plan must be added as an amendment to every test plan in circulation. All protocol changes must be reported to the ethics committee. In the case of changes to the study plan that are not exclusively of a formal nature and contain changes that are relevant to the test subject, a renewed vote of the ethics committee must be obtained. The patients / test persons must be informed of any changes to the study conditions as part of the information and consent. Any complications and serious adverse events in the course of the research project must be reported to the ethics committee immediately.

## **12. Ethical and Legal Issues**

When carrying out the study, in addition to the Declaration of Helsinki (as amended), the following guidelines and laws must be observed:

Medical Devices Act (MPG)

## **12. Insurance**

It is about eggno Non-interventional study (NIS). These studies were formerly known as the "Observatoryungen ". There was no study-specific increase in riskG, since there are no study-related interventions that go beyond clinical routine. No-fault insurance is taken out for the usual security and legal protection of employees.

## **13. Archiving and data protection**

The anonymisierThe most recent data are archived and backed up in accordance with the General Data Protection Regulation.

